4.5 Selection and Timing of Dose for Each Subject

At the time of entry into the lead-in period (Day -7 visit), the site will call IVRS in order for the lead-in medication to be assigned and dispensed. Subjects who successfully complete the lead-in period and meet the criteria for entry into the treatment period (see [Section 3.3](#)), will be randomly assigned by the IVRS to one of the following 3 double-blind treatment groups in a 1:1:1 ratio:

- BMS-986036 10 mg once daily (QD)
- BMS-986036 20 mg once weekly (QW)
- Placebo (QD)

Randomization will be stratified based upon diagnosis of Type 2 diabetes mellitus (yes vs. no).

The two strata for randomization are defined as follows:

- Strata 1: Diabetes Mellitus - Yes
- Strata 2: Diabetes Mellitus - No

Randomized subjects who discontinue will not be replaced.

Randomization schedules for both subject treatment and containers will be generated and kept by Bristol- Myers Squibb and stored in a secure location with restricted access.

At all study visits when study medication is dispensed, each subject will be assigned a kit number by the IVRS. Kit numbers will be assigned randomly and will correspond to the numbers printed on the packages and kits containing study drug. Kit numbers will be recorded on the appropriate eCRFs. The IVRS will be available 24 hours per day, 7 days per week.

4.6 Blinding/Unblinding

Blinding of treatment assignment is critical to the integrity of this clinical study. However, in the event of a medical emergency or pregnancy in an individual subject in which knowledge of the investigational product is critical to the subject's management, the blind for that subject may be broken by the investigator. The subject's safety takes priority over any other considerations in determining if a treatment assignment should be unblinded.

Before breaking the blind of an individual subject's treatment, the investigator should determine that the unblinded information is necessary, i.e., that it will alter the subject's immediate management. In many cases, particularly when the emergency is clearly not related to the investigational product, the problem may be properly managed by assuming that the subject is receiving active product. It is highly desirable that the decision to unblind treatment assignment be discussed with the Medical Monitor, but the investigator always has ultimate authority for the decision to unblind. The Principal Investigator should only call in for emergency unblinding AFTER the decision to discontinue the subject has been made.

In cases of accidental unblinding, contact the Medical Monitor and ensure every attempt is made to preserve the blind.

Any request to unblind a subject for non-emergency purposes should be discussed with the Medical Monitor.

In case of an emergency, the Investigator(s) has unrestricted access to randomization information via the IVRS and is capable of breaking the blind through the IVRS system without prior approval from sponsor. Following the unblinding the Investigator shall notify the Medical Monitor/ Study Director.

Also, designated staff of BMS Research and Development can be unblinded at any time. The Bioanalytical Sciences section or its designate will be unblinded to the randomized treatment assignments in order to minimize unnecessary analysis of samples from control group subjects. A single pharmacokineticist or designate in Clinical Pharmacology Pharmacometrics and a Biomarker scientist may be unblinded in order to prepare preliminary summaries of pharmacokinetic, pharmacodynamic, and safety data, as needed before data are more generally unblinded. These summaries will not reveal individual subjects' treatment assignments. Except as noted above, other members of BMS Research and Development will remain blinded.

4.6.1 Interim Analysis Unblinding

In the event of an Interim Analysis, the interim analyses will be performed by unblinded individuals. The access to unblinded interim individual data will be limited to pre-specified personnel (e.g. statistician, programmer, PK scientist, pharmacometrician and data integration programmer from Clinical Pharmacology and Pharmacometrics) as necessary to perform the interim analyses and data summaries. Except as noted above, other members of BMS Research and Development will remain blinded to individual subjects' data.

Data summaries will not reveal individual subjects' treatment assignments and will be presented using masked treatment codes. Data summaries will be provided to the following BMS personnel: Early Development Team Lead, Exploratory Clinical and Translational Research Therapeutic Area (TA) Head, PK TA Head, Statistical TA Head and Biomarker TA Head. The study team other than the aforementioned personnel will be blinded to data summaries.

4.7 Treatment Compliance

During the on-treatment phase, there will be a compliance check at each scheduled visit. The kit containing vials of study drug should be returned at each visit, and compliance will be assessed based upon an interview with the subject and a count of the vials. The Investigator (or designee) will record the amount of study drug dispensed and returned at each visit and the dates of any study drug interruption. During the double-blind treatment period, if the subject is $\leq 80\%$ compliant with study drug (BMS-986036/matching placebo) the period of noncompliance should be noted as a protocol deviation and the sponsor should be notified. The subject should be educated/properly instructed by designated site personnel on taking the study medication in accordance with the protocol.

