3.3.1 Inclusion Criteria

1. Signed Written Informed Consent

- a. Signed informed consent form.

2. Target Population

- a. Liver biopsy performed within 1 year of Screening or may be performed between Screening and Lead-in (Day -7) with documented results of NASH with NASH CRN fibrosis stage 1-3, or equivalent using a different scoring system.
- b. Body mass index (BMI) of ≥ 25 . Note: $BMI = \text{weight (kg)} / [\text{height (m)}]^2$
- c. Hepatic fat fraction (%) $\geq 10\%$ by MRI performed during the Screening period.
- d. Subject is able to medically tolerate the performance of the MRI or DXA scans and has suitable weight and circumference. See [Section 3.4.3](#) for further details.
- e. Subject agrees not to initiate a weight loss program and agrees to maintain consistent dietary habits and exercise regimen for the duration of the study.
- f. Subject re-enrollment: This study permits the re-enrollment of a subject that has discontinued the study as a pre-treatment failure (i.e., subject has not been randomized / has not been treated). If re-enrolled, the subject must be re-consented and will receive a new subject number.

3. Age and Reproductive Status

- a. Males and females, ages 21 to 75 years, inclusive
- b. Women of childbearing potential (WOCBP) must have a negative serum or urine pregnancy test (minimum sensitivity 25 IU/L or equivalent units of HCG) within 24 hours prior to the start of study drug.
- c. Women must not be breastfeeding.

- d. WOCBP must agree to follow instructions for method(s) of contraception for at least 4 weeks before dosing, for the duration of treatment with study drug (s) 16 weeks plus 5 half-lives of study drug (30 days) plus 30 days (duration of ovulatory cycle) for a total of 2 months post-treatment completion.
- e. Males who are sexually active with WOCBP must agree to follow instructions for method(s) of contraception for the duration of treatment with study drug (16 weeks) plus 5 half-lives of the study drug (30 days) plus 90 days (duration of sperm turnover) for a total of 4 months post-treatment completion.
- f. Azoospermic males and WOCBP who are continuously not heterosexually active are exempt from contraceptive requirements. However they must still undergo pregnancy testing as described in this section.

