4 STUDY DRUG

Study drug includes both Investigational [Medicinal] Product (IP/IMP) and Non-investigational [Medicinal] Product (Non-IP/Non-IMP) and can consist of the following:

- All products, active or placebo, being tested or used as a comparator in a clinical trial.
- Study required premedication, and
- Other drugs administered as part of the study that are critical to claims of efficacy (e.g., background therapy, rescue medications)
- Diagnostic agents: given as part of the protocol requirements must also be included in the dosing data collection.

BMS-986036 will be provided as a blinded solution for subcutaneous injection. Randomized subjects will self-administer double-blind treatment, once daily for 16 weeks, in an outpatient setting. Blinded treatment is supplied in Kits. Each Kit contains 8 vials, to support 1 week of treatment. 2 vials are provided for use on Day 1 of each week, and 1 vial is provided for use each day, on Days 2-7.

Once-daily treatment will consist of subcutaneous injection(s) administered in the abdomen. Subjects will be trained to rotate injection sites relative to the umbilicus. The time of dose administration will be called “0” hour, with regard to pre- and postdose clinical planned events. On clinic visit days, the morning injections are administered at the clinic, at a time determined by the Investigator to coordinate with the pre- and post-dose protocol specified clinical events scheduled for that clinic visit day. Treatment administration is described in Table 4-1.

Table 4-1: Treatment Administration

Treatment		Solution Strength	Number and volume of subcutaneous injections	
			Day 1 ^a of each treatment week	Days 2 - 7 of each treatment week
Lead-in phase	Placebo QD	N/A	2 x 1 mL	1 x 1 mL, daily
A	BMS-986036 10 mg QD	10 mg/ml	2 x 1 mL ^b	1 x 1 mL, daily
B	BMS-986036 20 mg QW	10 mg/ml	2 x 1 mL	1 x 1 mL, daily ^c
C	Placebo QD	N/A	2 x 1 mL	1 x 1 mL, daily

^a For all treatments, on Day 1 of each treatment week, two injections are administered concurrently, in the morning.

^b For treatment A, on Day 1 of each treatment week, the 2 injections consist of 1 active and 1 placebo, to maintain the blind between daily and weekly treatment arms.

^c For treatment B, on Days 2-7 of each treatment week, the injection is placebo, to maintain the blind between daily and weekly treatment arms.

Product description and storage information is described in [Table 4-2](#).

Table 4-2: Study Drugs for MB130045

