7.4 Extent of Exposure

Extent of exposure for 16-week double blinded treatment period will be summarized for all treated subjects, presenting the numbers and percentage of subjects with an extent of exposure within the following day ranges by treatment group: 1 to 15, 16 to 29, 30 to 43, 44 to 57, 58 to 86, 87 to 112 and > 112. Also the mean, SD, median and range of the extent of exposure to blinded treatment will be presented by treatment group. Study drug administration, randomization schedule will be documented as per subject listings. Any non-study medications taken by subjects, any conducted non-study medical treatment procedures, and any utilized non-study diagnostic procedures will also be listed.

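### Does the pooled 80% vial check need a separate Day 1 count, given that only 2 of 8 weekly-arm vials are active?

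*Protocol*

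**What the plan says.** Protocol 4.7 schedules a compliance check at every on-treatment visit: "compliance will be assessed based upon an interview with the subject and a count of the vials". The site also records drug dispensed and returned and the dates of any interruption. If a subject is at or below 80% "compliant with study drug (BMS-986036/matching placebo) the period of noncompliance should be noted as a protocol deviation", the sponsor is told and the subject is re-instructed. The section gives neither a formula (used over due, or used over dispensed) nor a counting period (per kit, per visit interval, or cumulative).

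Protocol 4 describes the supply: "Each Kit contains 8 vials, to support 1 week of treatment", two vials for Day 1 and one for each of Days 2-7. The footnotes to Table 4-1 show which are active. For the daily arm: "For treatment A, on Day 1 of each treatment week, the 2 injections consist of 1 active and 1 placebo". For the weekly arm: "For treatment B, on Days 2-7 of each treatment week, the injection is placebo". The same section adds: "On clinic visit days, the morning injections are administered at the clinic".

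On the analysis side, SAP 7.4 states: "Extent of exposure for 16-week double blinded treatment period will be summarized for all treated subjects". It uses day ranges, and it also provides by-subject listings of study drug administration. SAP 8.1.1 (PK Exclusions) allows subjects who missed doses to be left out of the PK analysis.

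**The concern.** The same pooled score stands for different active intake in the two arms. In the daily arm 7 of 8 vials are active, so the count follows active intake fairly closely. In the weekly arm all active drug sits in 2 of 8 vials, both used on one day, and the other six injections can hold the score up when that day is missed.

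Each active arm is compared with placebo at Week 16. If weekly-arm subjects lost much of their drug unnoticed, a weak weekly-arm result would be hard to read: poor regimen or poor intake? The day-range exposure table would not help, because these subjects inject placebo on the other days and still count as on treatment. The missing formula adds the possibility that sites score identical behaviour differently.

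**Working it through.** **Inputs.** Kit contents and active vials are from Protocol 4 and Table 4-1. Visits at D1, 15, 29, 43, 57, 86 and 112 are from Table 5.1-2. Weekly doses fall on D1 + 7k, giving 16 doses and 32 active vials. On nominal days, the weekly doses on D1, 15, 29, 43 and 57 are given in clinic, which leaves 16 - 5 = 11 at home.

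**Kit count.** 2 + 6 × 1 = 8 vials, as stated. Active share: daily arm 7/8, weekly arm 2/8.

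**Vials due per visit interval.** 16, 16, 16, 16, 34, 30 (total 128 = 16 × 8). Home Day 1 pairs: 1, 1, 1, 1, 4, 3 (total 11).

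**One home Day 1 pair missed in a two-week interval.** Score (16 - 2)/16 = 87.5%. Active drug lost: weekly arm 2/4 = 50%; daily arm 1/14 = 7%.

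**Dependence on the unstated formula** (most whole weekly doses missed without a flag):

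| Reading | Key scores | Maximum unflagged |
|---|---|---|
| Per weekly kit | one pair missed: 6/8 = 75%, flagged | 0 |
| Used / whole kits dispensed, assuming 2, 2, 2, 2, 5, 4 kits | D57-D85, one missed: 32/40 = 80.0%, flagged; D86-D112, two missed: 26/32 = 81.3% | 4 + 0 + 2 = 6 |
| Used / due per visit | D57-D85, three missed: 28/34 = 82.4%; D86-D112, two missed: 26/30 = 86.7%, three missed: 24/30 = 80.0%, flagged | 4 + 3 + 2 = 9 |
| Cumulative used / due | all 11 home pairs missed: 106/128 = 82.8% | 11 |

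The documents do not give the kit supply assumed in the second row. Every non-zero maximum needs a subject who skips Day 1 selectively and injects on the other days.

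**One of the two Day 1 injections taken, every home week.** Per visit: 15/16 = 93.8%, 30/34 = 88.2%, 27/30 = 90.0%. Per kit: 7/8 = 87.5%. Neither is flagged. Active drug lost: 11/32 = 34% in the weekly arm, at most 11/112 = 10% in the daily arm.

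**Omission without a Day 1 preference.** 200,000 simulated subjects; home injection days missed independently; clinic doses taken; used / due per visit.

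| Days missed | Unflagged | Of these, weekly-arm active intake ≤ 80% | Expected in 30 subjects | Mean active intake, unflagged: weekly / daily |
|---|---|---|---|---|
| 5% | 96.0% | 0.10% | 30 × 0.960 × 0.0010 = 0.03 | 96.8% / 95.4% |
| 10% | 69.1% | 0.59% | 30 × 0.691 × 0.0059 = 0.12 | 94.6% / 91.5% |
| 15% | 29.0% | 0.85% | 30 × 0.290 × 0.0085 = 0.07 | 93.8% / 88.7% |

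Among unflagged subjects, mean active intake is no lower in the weekly arm than in the daily arm, partly because 5 of its 16 doses are given in clinic.

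**Cover from serum samples.** Protocol 3.3.1 equates "5 half-lives of study drug (30 days"), so take a half-life of 30/5 = 6 days and assume first-order decline. With r = 0.5^(7/6) = 0.445 and n weekly doses before the sample, missing the latest one lowers the sample by (1 - r)/(1 - r^n):

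- D15 (n = 2): 69%
- D29 (n = 4): 58%
- D43 (n = 6): 56%
- D57 (n = 8): 56%
- D86 (n = 13, dose on D85): 55%
- D112 (n = 16, dose on D106): 55%

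The latest home dose in each of the six intervals, 6 of 11, is therefore probed directly. A half dose gives half of each fall. In the nine-dose case, any three of four misses in D57-D85 lower the D86 value by at least 41%, and any two of three in D86-D112 lower the D112 value by at least 36%.

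**What uses the flag.** Neither Protocol 8.2 nor SAP 6.3 defines a per-protocol population. The primary model (SAP 7.5) takes treated subjects with a baseline and at least one post-baseline measurement. The PK exclusion wording refers to missed doses and does not mention the 80% score.

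**The case for a change.** The strongest case for a change does not rest on deliberate skipping. Day 1 is the only two-injection day, so taking one injection instead of two is a believable habit. It escapes both the per-visit and the per-kit reading and costs the weekly arm 34% of its active drug. Sampling is thinnest where this could run longest: 7 of the 11 home weekly doses fall after D57 and only two pre-dose samples follow them. No stated rule ties the diary or interruption dates to Day 1. A Day 1 line recorded identically in all arms would keep the blind.

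Much of this stands. The pooled count can miss such a pattern, and the formula should have been written down. It does not show that a planned result would differ. With or without a flag, the subject stays in the same analyses. Missed doses can be looked for in the interview, the diary reviewed at each visit, the interruption dates and the dosing listings. Active intake by arm can be computed from recorded dosing after unblinding without a protocol change. It also cannot be said that no such table is planned, since the Data Presentation Plan and SAP Appendix 1 are not in the text available. The proposed Day 1 line would carry no threshold and trigger no analysis. How easily sites could complete it is unknown, because the documents describe neither day-labelled vials nor diary fields.

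The serum argument has limits too. Between-subject variability is not given, so a lower trough is supporting evidence and not proof.

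**Conclusion.** No change is needed. The 2-of-8 against 7-of-8 contrast is real, and on a per-visit count one missed home Day 1 pair passes at 87.5%. Whether that happens depends on a counting period that Protocol 4.7 leaves open, since the per-kit count flags it at 75%. Sites and analysts can settle that sensibly.

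The flag is a site-management prompt. It feeds no analysis population and no model, so the Week 16 comparison is the same either way. Without a Day 1 preference, the expected number of unflagged weekly-arm subjects at or below 80% active intake is 0.03 to 0.12 in 30. Larger losses need selective Day 1 omission or a persistent one-injection habit, and several records already collected could show either.

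These figures assume nominal visit and dose days, clinic doses taken as scheduled and, for the simulation, independent omission scored as used / due per visit. The sample reductions also assume a 6-day half-life and first-order decline.

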4.8 Destruction of Study Drug

For this study, study drugs (those supplied by BMS or sourced by the investigator) such as partially used study drug containers, vials and syringes may be destroyed on site.

Any unused study drugs can only be destroyed after being inspected and reconciled by the responsible BMS Study Monitor unless study drug containers must be immediately destroyed as required for safety, or to meet local regulations (e.g., cytotoxics or biologics).

On-site destruction is allowed provided the following minimal standards are met:

- On-site disposal practices must not expose humans to risks from the drug.
- On-site disposal practices and procedures are in agreement with applicable laws and regulations, including any special requirements for controlled or hazardous substances.
- Written procedures for on-site disposal are available and followed. The procedures must be filed with the site's SOPs and a copy provided to BMS upon request.
- Records are maintained that allow for traceability of each container, including the date disposed of, quantity disposed, and identification of the person disposing the containers. The method of disposal, i.e., incinerator, licensed sanitary landfill, or licensed waste disposal vendor must be documented.
- Accountability and disposal records are complete, up-to-date, and available for the Monitor to review throughout the clinical trial period.

If conditions for destruction cannot be met the responsible BMS Study Monitor will make arrangements for the return of study drug.

It is the investigator's responsibility to arrange for disposal of all empty containers, provided that procedures for proper disposal have been established according to applicable federal, state, local, and institutional guidelines and procedures, and provided that appropriate records of disposal are kept.

4.9 Return of Study Drug

If study drug will not be destroyed upon completion or termination of the study, all unused and/or partially used study drug that was supplied by BMS must be returned to BMS. The return of study drug will be arranged by the responsible Study Monitor.

It is the investigator's responsibility to arrange for disposal of all empty containers, provided that procedures for proper disposal have been established according to applicable federal, state, local, and institutional guidelines and procedures, and provided that appropriate records of disposal are kept.

Arrangements for the return of study drug will be made by the responsible Study Monitor.

5 STUDY ASSESSMENTS AND PROCEDURES

5.1 Flow Chart/Time and Events Schedule

Study assessments and procedures are presented in [Table 5.1-1](#), [Table 5.1-2](#) and [Table 5.1-3](#).

Table 5.1-1: Screening Procedural Outline (MB130045)

Procedure	Screening	Lead-in	Notes
	D-42 to D-8	D-7	
Visit Window (days)		+/- 2	
Eligibility Assessments			
Informed Consent	X		A subject is considered part of the study only when a protocol specific informed consent is signed.
Inclusion/Exclusion Criteria	X	X	
Medical History	X		Include any toxicities or allergy related to previous treatments.
Liver biopsy	X		Performed within 1 year of screening or between Screening and Lead-in. Must be NASH CRN fibrosis stage 1 to 3, or equivalent.
Patient education: subcutaneous injection and diary usage		X	Patients will be educated on the techniques/use of subcutaneous injection and patient diary. Subjects may return for additional visits during the Lead-in phase, if the subject or the site feels additional education/instruction is required. The Investigator will review subject diary, placebo compliance, and assess self-injection skills on Day 1 BEFORE randomizing the subject in IVRS.
Practice at Home		X (D-7 to D-1)	Subcutaneous placebo injection and diary use (once per day) from Day -7 to Day -1.
Imaging Facility Assessments			
Dual-emission X-ray Absorptiometry (DXA)	X		Performed approximately 21 days prior to the Day 1 dose. Eligibility should be confirmed by central imaging lab prior to entry into the lead-in period (Day -7). Bone imaging (hip and lumbar spine) performed at all imaging facilities. Body composition (whole body), an exploratory measure, will be additionally carried out at imaging facilities with the appropriate hardware/software.
Magnetic Resonance Imaging (MRI)	X		Performed approximately 21 days prior to the Day 1 dose. Eligibility should be confirmed by central imaging lab prior to entry into the lead-in period (Day -7).
Safety Assessments			
Physical Examination (PE)	X		To include general appearance, head, eyes, ears, nose, throat, neck, cardiovascular, lungs, abdomen, lymph nodes, and extremities, neurological, skin, and musculoskeletal.
Targeted PE		X	A targeted physical exam should be performed by the investigator or qualified professional. It includes assessment of heart, lung, abdomen and injection site reactions (as measured by the Draize Scale for erythema and edema (see Section 5.3.3) and should also be guided by the examiner's observations and/or patient complaints on new or changed conditions,

Table 5.1-1: Screening Procedural Outline (MB130045)

Procedure	Screening	Lead-in	Notes
	D-42 to D-8	D-7	
			symptoms or concerns.
Physical Measurements	X	X	Weight, BMI and waist circumference measurement. See Section 5.9 Height at screening only.
Vital Signs	X		Includes body temperature, respiratory rate, seated blood pressure and heart rate. Blood pressure and heart rate should be measured after the subject has been seated quietly for at least 5 minutes.
Electrocardiogram (ECGs)	X		ECGs should be recorded after the subject has been supine for at least 5 minutes. ECG parameters including QTcF will be collected on the CRF.
IVRS Call	X	X	IVRS call to be conducted on the day of each subject visit where indicated
Laboratory Tests (hematology, clinical chemistry, urinalysis, INR)	X		Subjects are required to fast for at least 10 hours prior to the collection of specimens for clinical laboratory tests.
Pregnancy Testing	X		Female subjects of child bearing potential. Serum pregnancy testing performed at screening
██████████	█		
Lipid panel	X		Triglycerides, total cholesterol, LDL and HDL
FSH	X		In women <55 years, to confirm menopause.
Clinical Drug Supplies			
Dispense Lead-in supply		X	
Review injection technique		X	
Adverse Event Reporting			
Monitor for Non-Serious Adverse Events		X	All non-serious AEs will be collected from the start of the Lead-In phase until 30 days after discontinuation of dosing. AEs should be followed to resolution or stabilization.
Monitor for Serious Adverse Events	X	X	All SAEs must be collected from the date of subject's written consent until 30 days after discontinuation of dosing. In addition, the investigator should report any SAE that occurs after 30 days post-dosing that is believed to be related to study drug or protocol-specified procedure

Abbreviations: D = Day

Table 5.1-2: On Treatment Procedural Outline (MB130045)

Procedure	D 1	D 15	D 29	D 43	D 57	D 86	End of Treatment D 112	Early Termination Visit ^a	Notes
Clinic Visit Window (days)	0	+3	+3	+3	+3	+3	-3		
Patient education: subcutaneous injection and diary usage	X								The Investigator will review subject diary, placebo compliance, and assess self-injection skills on Day 1 BEFORE randomizing the subject.
IVRS call	X	X	X	X	X	X	X	X	IVRS call to be conducted on the day of each subject visit
Randomize	X								Predose on Day 1.
Safety Assessments									
Inclusion/Exclusion Criteria	X								Predose on Day 1.
Physical Examination (PE)	X						X	X	Predose on Day 1. Injection site reactions (as measured by the Draize Scale for erythema and edema (see Section 5.3.3))
Targeted PE		X	X	X	X	X			See note in screening procedures.
Physical Measurements	X	X	X	X	X	X	X	X	Weight, BMI and waist circumference measurement. Weight must be recorded using a calibrated scale. Predose on Day 1.
Vital Signs	X	X	X	X	X	X	X	X	See note in screening procedures.
Electrocardiogram (ECGs)	X						X	X	See note in screening procedures, or as clinically indicated.
Laboratory Tests (hematology, clinical chemistry, urinalysis, INR)	X	X	X	X	X	X	X	X	Pre-dose on Day 1. See note in screening procedures and Section 5.3.2 .
Pregnancy Testing	X		X		X	X	X	X	Female subjects of child bearing potential. Urine pregnancy testing performed at all specified visits, with a reflex to serum pregnancy testing if urine pregnancy testing is positive.
Dual-emission X-ray Absorptiometry (DXA)							X	X	Window +/- 1 week Bone imaging (hip and lumbar spine) at all imaging facilities.
Adverse Event Reporting									
Monitor for Non-Serious Adverse Events	X	X	X	X	X	X	X	X	Day 1 assessment occurs after study drug administration.
Monitor for Serious Adverse Events	X	X	X	X	X	X	X	X	See note in screening procedures.
Efficacy Assessments									
MRI					X		X	X	MRI should be conducted within +/- 1 week. At early termination, MRI conducted only if subject received ≥ 6 weeks of study drug and was ≥ 1 month from previous MRI.

Table 5.1-2: On Treatment Procedural Outline (MB130045)

Procedure	D 1	D 15	D 29	D 43	D 57	D 86	End of Treatment D 112	Early Termination Visit ^a	Notes
Pharmacokinetic (PK) Assessments									
PK Sampling	See Table 5.5.1-1								
Immunogenicity testing	See Table 5.5.1-1								Refer to Section 5.7
[REDACTED]									[REDACTED]
[REDACTED]									[REDACTED]
Clinical Drug Supplies									
Review injection technique	X								
Dispense Study Drug	X	X	X	X	X	X			Supplied by BMS.
Blinded drug administration	X	X	X	X	X	X	X		Blinded treatment will be administered at the site on clinic visit days.
Patient diary review	X	X	X	X	X	X	X	X	
^a Early Termination is not a scheduled visit. For early termination PK and PD assessments, refer to Table 5.5.1-1 Abbreviations: D = Day									

Table 5.1-3: Post Treatment Follow-up Procedural Outline (MB130045)

Procedure	D 142 (30 days after last dose)	D 292 (6 mo after last dose)	Follow-up for immunogenicity ^a (up to 12 months post Day 142)	Early Termination Visit ^b	Notes
Visit Window	+/- 3 days	+/-2 wk	n/a		
IVRS Call	X			X	
Safety Assessments					
Physical Examination	X			X	
Targeted Physical Examination					Injection site reactions (as measured by the Draize Scale for erythema and edema (see Section 5.3.3), others as clinically indicated. See note in Screening procedures.
Physical Measurements	X			X	Weight (using calibrated scale), BMI and waist circumference measurement.
Vital Signs	X			X	See note in screening procedures.
Electrocardiograms (ECGs)	X			X	See note in screening procedures.
Laboratory Tests (hematology, clinical chemistry, urinalysis, INR)	X			X	See note in screening procedures.
Pregnancy Testing	X			X	Female subjects of child-bearing potential. Urine pregnancy testing to be performed at post treatment specified visits with reflex to serum if urine pregnancy testing is positive.
Dual-emission X-ray Absorptiometry (DXA)		X			Bone imaging (hip and lumbar spine) at all imaging facilities.
Adverse Event Reporting					
Monitor for Adverse Events	X			X	Up to 30 days after the last dose.
Monitor for Serious Adverse Events	X			X	See note in screening procedures.
Pharmacokinetic (PK) Assessments					
PK Sampling	X	X			Refer to Table 5.5.1-1
Immunogenicity testing	X	X	X	X	Refer to Table 5.5.1-1 and Section 5.7
████████████████████	██████████				
██████████	██████████				

^a Applies only to subjects with positive immunogenicity at D142 and/or D292. (Refer to [Section 5.7](#)). These immunogenicity follow-up visits will commence after D142 or D292, if immunogenicity results are positive at D142 or D292, respectively, without evidence of decreasing or stable antibodies.

^b Early Termination is not a scheduled visit. For early termination PK and PD assessments, refer to [Table 5.5.1-1](#)

Abbreviations: D = Day

